#### **8.4.2.1.4 Analysis of Safety Laboratory Values**

This study has no safety laboratory values.

#### **8.4.2.2 Analysis of Primary Efficacy Objective(s)**

This study has no efficacy objectives.

#### **8.4.2.2.1 Statistical Hypotheses**

Not applicable

#### **8.4.2.2.2 Analysis Sets**

Not applicable.

#### **8.4.2.2.3 Statistical Methods**

Not applicable.

### **8.4.2.3 Analysis of Primary Immunogenicity Objective(s)**

The frequency and percentages of subjects with serotype-specific (Ia, Ib, and III) antibody concentrations above a set of pre-defined sequential serotype-specific serum antibody levels and associated two-sided 95% Clopper-Pearson CIs will be computed for each study group, for the MF59 study groups combined, for the unadjuvanted and Alum adjuvanted study groups combined, and the placebo and naïve groups combined for concentrations at day 61 post-vaccination.

Differences in percentages between study groups will be computed and two-sided 95% confidence intervals for the difference constructed using the method of Miettinen and Nurminen. The following treatment group comparisons will be examined: each 5 µg group compared to the placebo group from study V98\_06 and separately to the naïve group; the combined MF59 groups compared to the combined placebo and naïve groups; and, the combined unadjuvanted and Alum groups compared to the combined placebo and naïve groups.

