**Secondary Endpoints:**

The serotype-specific (Ia, Ib, and III) geometric mean antibody as measured by ELISA at days 31 and 61 post-vaccination in study V98\_06E1 in all subjects and by pre-vaccination serotype-specific GBS antibody LLQ status in the V98\_06 study or V98\_06E1 study for the naive group.

The percentage of subjects reaching pre-defined sequential serotype-specific serum antibody levels for serotypes Ia, Ib and III at day 31 post vaccination as measured by ELISA in all subjects

The percentage of subjects reaching pre-defined sequential serotype-specific serum antibody levels for serotypes Ia, Ib and III at day 31 and 61 post vaccination as measured by ELISA in subjects according to pre-vaccination serotype-specific GBS antibody LLQ status in the V98\_06 study or V98\_06E1 study for the naive group.

The within subject geometric mean ratio (GMR) of serotype-specific (Ia, Ib & III) serum

Name of Sponsor: GlaxoSmithKline Biologicals S.A.	Protocol number: V98_06E1	Generic name of study vaccine: GBS Trivalent Vaccine
--	-------------------------------------	--

antibody levels as measured by ELISA at day 31 and 61. The GMRs will be determined relative to pre-vaccination in V98\_06E1 and separately relative to pre-vaccination in V98\_06 for groups except the naive group. The GMRs will be determined for all subjects and by pre-vaccination serotype-specific GBS antibody LLQ status in the V98\_06 study or V98\_06E1 study for the naive group.

Reverse cumulative distribution function (RCDF) curves of serotype-specific (Ia, Ib and III) serum antibody levels, as measured by ELISA, at pre-vaccination in V98\_06 study or V98\_06E1 study for the naive group, vaccination and day 31 and 61 post-vaccination in all subjects and by pre-vaccination serotype-specific GBS antibody LLQ status in the V98\_06 study or V98\_06E1 study for the naive group.

The anti-diphtheria geometric mean antibody concentrations measured by ELISA for samples collected before the first vaccination with GBS Trivalent Vaccine in the V98\_06 study or V98\_06E1 study for the naive group and on day 31 and day 61 post vaccination in V98\_06E1.

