### **7.3 Immunogenicity Assessment**

For the primary and secondary immunogenicity objectives, the GBS serotype-specific (Ia, Ib, III) IgG antibody responses in the serum will be determined by ELISA.

Original samples from subjects who participated in the V98\_06 study who are also participating in this V98\_06E1 study may be re-tested for the purposes of consistency in the ELISA assay being used to analyze the samples collected in this extension study.

The GBS serotype-specific IgG ELISAs in sera will be carried out by Clinical Laboratory Sciences, GlaxoSmithKline, Marburg, Germany.

The diphtheria-specific IgG antibody levels will be measured by ELISA. Testing will be conducted by a designated, qualified external laboratory.

Functional activities of anti-GBS antibodies will be measured by opsonophagocytic killing assay (OPK). Testing will be conducted by a designated qualified external laboratory.

Technical details (or instructions) for specimen collection, processing and shipment will be described in Clinical Specimen Lab Manual which will be made available to site

personnel after site initiation (e.g. refer to the Clinical Specimen Lab Manual in the investigator site file).

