### **8.1.2.3 Secondary Immunogenicity Endpoint(s)**

The secondary immunogenicity endpoints are:

The percentage of subjects reaching pre-defined sequential serotype-specific (Ia, Ib and III) serum antibody levels as measured by ELISA at other time points and in subgroups of subjects defined by their pre-vaccination serotype-specific GBS antibody LLQ status in the V98\_06 study (or the V98\_06E1 study for the naive group).

The serotype-specific (Ia, Ib, and III) geometric mean concentrations (GMCs) as measured by ELISA at days 31 and 61 post-vaccination in study V98\_06E1 and in the subgroups of subjects defined according to their pre-vaccination serotype-specific GBS antibody LLQ status in the V98\_06 study (or V98\_06E1 study for the naive group).

The within subject geometric mean ratio (GMR) of serotype-specific (Ia, Ib & III) serum antibody levels as measured by ELISA at day 31 and 61. The GMRs will be determined relative to pre-vaccination in V98\_06E1 and separately relative to pre-vaccination in V98\_06 for all groups except the naive group. The GMRs will also be determined for subgroups of subjects defined according to their pre-vaccination serotype-specific GBS antibody LLQ status in the V98\_06 study or V98\_06E1 study for the naive group.

Reverse cumulative distribution function (RCDF) curves of serotype-specific (Ia, Ib and III) serum antibody levels, as measured by ELISA, at pre-vaccination in V98\_06 study or V98\_06E1 study for the naive group, vaccination, day 31 and day 61 post-vaccination in all subjects and by pre-vaccination serotype-specific GBS antibody LLQ status in the V98\_06 study or V98\_06E1 study for the naive group.

The anti-diphtheria geometric mean antibody concentrations measured by ELISA for samples collected before the first vaccination with GBS Trivalent Vaccine in the V98\_06 study or V98\_06E1 study for the naive group and on day 61 post-vaccination in V98\_06E1.

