### **8.3.7 Subgroups**

Subgroups of subjects will be created based on the ELISA serotype-specific (Ia, Ib, III) antibody LLQ status prior to initial vaccination in study V98\_06 (or V98\_06E1 for the naive group).

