## **8.4 Statistical Analysis Plan**

### **8.4.1 Analysis of Demographic and Baseline Characteristics**

Descriptive statistics (mean, standard deviation, median, minimum and maximum) for age, height and weight at enrolment will be calculated overall and by vaccine group.

Distributions of subjects by sex, race, ethnic origin, V98\_06 vaccine formulation group (or naïve) and pre-vaccination LLQ status will be summarized overall and by vaccine group.

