##### **8.4.3.3.3 Statistical Methods**

*GBS*

*Percentages at Day 31 and RCDFs*

The frequency and percentages of subjects with serotype-specific concentrations above a set of pre-defined sequential serotype-specific (Ia, Ib and III) serum antibody levels and associated two-sided 95% Clopper-Pearson CIs will be computed for each study group, for the MF59 study groups combined, for the unadjuvanted and Alum adjuvanted study groups combined, and the placebo and naive groups combined for concentrations at day 31 post-vaccination. Differences in percentages between study groups will be computed and two-sided 95% confidence intervals for the difference constructed using the method of Miettinen and Nurminen. Differences in percentages between study groups will be computed and two-sided 95% confidence intervals for the difference constructed using the method of Miettinen and Nurminen. The following treatment group comparisons will be examined: each 5µg group compared to the placebo group from study V98\_06 and separately to the naïve group; the combined MF59 groups compared to the combined

placebo and naïve groups; and, the combined unadjuvanted and Alum groups compared to the combined placebo and naïve groups.

Similar analyses will be performed for the subset of subjects defined by the pre vaccination serotype-specific GBS antibody LLQ status in the V98\_06 study or V98\_06E1 study for the naïve group.

The percentages of subjects with serotype-specific concentrations above a set of pre-defined sequential serotype-specific serum antibody levels will be graphically displayed as RCDFs.

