#### *Geometric Mean Concentrations*

Before any statistical analysis that assumes normally distributed observations, antibody concentrations will be  $\log_{10}$ -transformed. Individual concentrations below the limit of quantitation (LLQ) will be set to half that limit.

The logarithmically (base 10) transformed antibody concentrations will be modeled using an analysis of covariance (ANCOVA) model with a qualitative factor for vaccine group and  $\log$  (base 10) pre-vaccination concentration in study V98\_06, or V98\_06E1 for the naïve group, as a covariate. As this is a single-center study, site is not included as a covariate. Response in the V98\_06 study was different in those with a pre-vaccination concentration below the LLQ, so pre-vaccination concentration is included. The adjusted GMC and the two-sided, 95%, confidence intervals (CIs) of the GMC will be calculated based on this model. The ratio of GMCs and the corresponding two-sided, 95% CI will also be calculated based on this model. The adjusted GMC and two-sided 95% CIs will be constructed by exponentiation (base 10) of the least square means of the logarithmically transformed (base 10) antibody concentration. The model can be written as:

$$\log_{10}(y_{ik}) = \mu + \alpha_i + \beta x_{ik} + \varepsilon_{ik}$$

where  $\mu$  represents a common overall mean,  $\alpha_i$  represents the vaccine group  $i$  effect (where vaccine group is either the V98\_06 vaccine group, or naïve),  $\beta$  represents the common slope for the  $\log_{10}$  prevaccination concentration,  $x_{ik}$  for subject  $k$  in vaccine group  $i$ , and  $\varepsilon_{ik}$  represents random error for subject  $k$  in vaccine group  $i$ . A similar approach will be used in the subgroups based on pre-vaccination LLQ status.

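### The day 61 and day 31 differences in percentages are unadjusted; an LLQ-stratified difference should be reported beside them

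*Combined protocol and SAP*

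**What the plan says.** Section 8.4.2.3, on the primary day 61 percentages, states: "Differences in percentages between study groups will be computed and two-sided 95% confidence intervals for the difference constructed using the method of Miettinen and Nurminen". It lists each of the four 5 µg groups against placebo and separately against naive subjects, then the pooled MF59 groups and the pooled unadjuvanted and Alum groups, each against placebo and naive combined. Section 8.4.3.3.3 repeats this for day 31. Neither names a stratifier, weight or covariate.

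For GMCs, section 8.4.3.3.3 does adjust. It says that response in the V98_06 "study was different in those with a pre-vaccination concentration below the LLQ, so pre-vaccination concentration is included".

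LLQ status enters the percentages in other ways:

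- Section 8.3.7: "Subgroups of subjects will be created based on the ELISA serotype-specific (Ia, Ib, III) antibody LLQ status prior to initial vaccination". Status comes from V98_06 for returning subjects and from V98_06E1 for naive subjects.
- Section 8.4.1: "pre-vaccination LLQ status will be summarized overall and by vaccine group".
- The synopsis secondary endpoints include the percentage reaching the "serum antibody levels for serotypes Ia, Ib and III at day 31 and 61 post vaccination as measured by ELISA in subjects according to" LLQ status. Section 8.1.2.3 has percentages "at other time points and in subgroups of subjects defined by their pre-vaccination serotype-specific GBS antibody LLQ status". The synopsis statistical analyses also list LLQ-status groups for the percentages, day 61 included.
- Section 8.4.3.3.3, under its day 31 heading: "Similar analyses will be performed for the subset of subjects defined by the pre vaccination serotype-specific GBS antibody LLQ status".

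On the assay, section 7.3 says original V98_06 samples "may be re-tested for the purposes of consistency in the ELISA assay being used to analyze the samples collected in this extension study".

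**The concern.** The plan treats pre-vaccination LLQ status as prognostic and adjusts the GMCs for it, but leaves the between-group differences on the primary endpoint's percentages unadjusted. A percentage above a level is a cut of the same concentration distribution, so the GMC reasoning plausibly carries over. That is an inference: the plan's statement sits in the GMC text and gives no size.

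Groups in this extension are not randomised. Imbalance is most plausible where naive subjects enter the comparison. The active v placebo contrasts keep their origin in the parent randomisation (section 1.2), subject to selective return.

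If LLQ mix differs, the crude difference combines that imbalance with the effect of the earlier dose. A reader would see the imbalance in the baseline table and the results by stratum, but no pre-specified overall figure showing how much it matters. What is at stake is confounding of a descriptive estimate, not type I error.

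**Working it through.** **Inputs.** The documents give no LLQ shares, response rates or effect sizes, so there is no plan figure to reproduce. Group sizes come from Table 3-1: up to 40 in each of five parent-study groups plus 20 naive (5 × 40 + 20 = 220). One active group v naive is at most 40 v 20; a pooled contrast is at most 80 v 60. Everything else is assumed.

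**Contrasts per serotype and level.** 4 active v placebo + 4 active v naive + 2 pooled = 10. Those including naive subjects: 4 + 2 = 6.

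**Shift when the true within-stratum difference is zero.** Shift = response gap between strata × difference in share below LLQ.

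| Response gap | Shares differ by 10 | by 20 | by 30 |
|---|---|---|---|
| 20 points | 2 | 4 | 6 |
| 40 points | 4 | 8 | 12 |
| 60 points | 6 | 12 | 18 |

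Check of the middle case, with response 50% below and 90% above LLQ and shares below of 60% and 40%: 0.6 × 0.5 + 0.4 × 0.9 = 0.66, against 0.4 × 0.5 + 0.6 × 0.9 = 0.74, a gap of 8 points.

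**Worked example, 40 v 40.** Same response rates, with 50% v 75% below LLQ. Crude: 28/40 − 24/40 = +10.0 points (Miettinen-Nurminen 95% CI −11.0 to +30.2). By stratum: 18/20 v 9/10 and 10/20 v 15/30, both zero, so the Mantel-Haenszel difference is 0.0.

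**Coverage of the crude 95% interval** (simulated, true difference zero, random LLQ counts). Mild is gap 20 and share difference 10; middle is 40 and 20; worst is 60 and 30.

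| Sizes | Mild | Middle | Worst |
|---|---|---|---|
| 20 v 10 | 96% | 94% | 85% |
| 40 v 20 | 95% | 92% | 73% |
| 40 v 40 | 95% | 88% | 62% |
| 80 v 60 | 94% | 83% | 42% |

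Varying the direction of imbalance and taking LLQ counts as fixed or random, the middle case runs 90–94% at 40 v 20 and 82–86% at 80 v 60. The stratified interval covers 95–96% throughout. At small sizes the crude interval is wide enough to absorb much of the shift: at 70% v 70% its width is 67 points at 20 v 10, 48 at 40 v 20 and 31 at 80 v 60.

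**Limit 1: misclassified LLQ status.** Take 40 returners v 20 naive, true shares 50/50, response 50/90%, and 10% of truly-below returners recorded as above. Returners then show 18 below and 22 above, with response above of (20 × 0.9 + 2 × 0.5)/22 = 0.864 against 0.90 in naive subjects. The weights are 18 × 10/28 = 6.43 below and 22 × 10/32 = 6.88 above, so the bias is 0.036 × 6.88/13.31, about 1.9 points; at 20% misclassified it is about 3.6. The crude bias is zero here. At a true 20-point share difference the stratified estimate is off by 1.2–2.9 points (10% misclassified) or 2.4–5.3 (20%), against 8 for the crude.

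**Limit 2: unlike effects across strata.** Suppose the effect is +20 points below LLQ and 0 above, at 40 v 20. With shares below of 60% active and 40% control, the weights are 24 × 8/32 = 6 below and 16 × 12/28 = 6.86 above, so the stratified difference is 20 × 6/12.86 = 9.3 points; with shares reversed it is 10.7. The crude figures are 4 and 16. With a common share, the stratified difference is 20 × share: 4 points at 20% and 16 at 80%. The stratum figures are therefore needed as well.

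**Sparse strata.** With 10 controls, the chance that a stratum is empty among them runs from 2 × 0.5¹⁰ = 0.2% (share 50%) to 0.8¹⁰ = 11% (share 20% or 80%), and of 2 or fewer subjects from 11% to 68%. With 20 controls these are 0–1% and 0–21%. Counting either arm at a 20% share, an empty cell has probability 12% at 20 v 10 and 20% at 10 v 10; for a cell of 2 or fewer, 74% and 90%.

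**The case against.** The strongest reply is that the plan already handles LLQ status: results by stratum at both days, LLQ mix by group, baseline-adjusted GMC ratios, and the synopsis analysis list that includes day 61. On this view only one summary number is missing, and reporting strata without pooling is a legitimate descriptive choice. This partly stands, and is why the point is minor. But the synopsis list mentions no differences in percentages, and within-subset differences are written out only under the day 31 heading. The only planned repeat of the primary analysis is in the FAS, which changes the analysis set and adjusts nothing.

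A second reply is that the stratified figure is weakest where it is most wanted. In contrasts with naive subjects, returners are classified on samples taken 4–6 years earlier, and re-testing is optional. Misclassification can bias the stratified estimate when the crude one is unbiased, and unlike effects make it depend on LLQ mix. Both points stand, and they are reasons to show crude, stratified and stratum-specific results together.

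Third, every magnitude is assumed. At 20 v 10 and 40 v 20, crude coverage in the mild and middle cases is 90–96%; the 42% figure needs the worst inputs and full enrolment, while section 1.2 warns that numbers may be limited. That stands too. Sparse strata are also likelier once both arms are counted, so a rule for them is needed.

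**Conclusion.** The gap is real: neither section plans an LLQ-adjusted overall difference in percentages, although the plan adjusts the GMCs for the same prognostic factor. The possible shift is 0 to 18 points over the assumed range, with 8 points in the middle case. All of this rests on assumed response gaps and LLQ shares and on carrying the GMC statement over to percentages.

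This is a worthwhile improvement, not a defect that threatens the study. The primary immunogenicity endpoint is the percentages themselves, and there are no hypotheses or success criteria. Other differences between returning and naive subjects would remain unadjusted. Sections 8.3.8 and 8.4.2.1.2 defer some details to a statistical analysis plan, so the conclusion covers only the combined document reviewed. Confidence is medium.

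**What to change.** Keep the crude difference. In section 8.4.2.3, and in the day 31 text of 8.4.3.3.3:

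- Report beside it a Miettinen-Nurminen difference stratified by serotype-specific pre-vaccination LLQ status as defined in 8.3.7, with Mantel-Haenszel weights.
- Show the stratum-specific differences at both day 31 and day 61.
- State in advance how a stratum with an empty arm is handled.
- Base LLQ status on V98_06 samples re-tested in the same ELISA where re-testing is done; otherwise flag possible misclassification between returners and naive subjects.

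The cost is wording and table rows, with no new data. The stratified differences number 10 contrasts × 3 serotypes = 30 per antibody level for each of day 61 PPS, day 61 FAS and day 31 PPS, or 90 per level. Stratum-specific differences at day 61 add 30 × 2 = 60 per level. The number of levels is not given.

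Precision is little affected. At 40 v 20 with equal shares and a 40-point gap, the stratified SE is smaller (0.114 v 0.125 crude). With a 20-point gap and a 30-point share difference it is slightly larger (0.128 v 0.124).

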#### **8.4.2.3.1 Statistical Hypotheses**

There are no statistical hypotheses. All analyses are descriptive.

#### **8.4.2.3.2 Analysis Sets**

The primary immunogenicity analyses will be based on the per-protocol set (PPS) at day 61. The primary analyses will be repeated using the Full Analysis Set (FAS) as a measure of the sensitivity/robustness of the results (further details are given in [section 8.3](#)).

#### **8.4.2.3.3 Statistical Methods**

### **8.4.3 Analysis of Secondary Objective(s)**

#### **8.4.3.1 Analysis of Secondary Safety Objective(s)**

There are no secondary safety objectives.

##### **8.4.3.1.1 Statistical Methods**

#### **8.4.3.2 Analysis of Secondary Efficacy Objective(s)**

This study has no efficacy objectives.

#### **8.4.3.3 Analysis of Secondary Immunogenicity Objective(s)**

##### **8.4.3.3.1 Statistical Hypotheses**

There are no statistical hypotheses. All analyses are descriptive.

##### **8.4.3.3.2 Analysis Sets**

The secondary immunogenicity analyses will be based on the per-protocol set (PPS).

##### **8.4.3.3.3 Statistical Methods**

*GBS*

*Percentages at Day 31 and RCDFs*

The frequency and percentages of subjects with serotype-specific concentrations above a set of pre-defined sequential serotype-specific (Ia, Ib and III) serum antibody levels and associated two-sided 95% Clopper-Pearson CIs will be computed for each study group, for the MF59 study groups combined, for the unadjuvanted and Alum adjuvanted study groups combined, and the placebo and naive groups combined for concentrations at day 31 post-vaccination. Differences in percentages between study groups will be computed and two-sided 95% confidence intervals for the difference constructed using the method of Miettinen and Nurminen. Differences in percentages between study groups will be computed and two-sided 95% confidence intervals for the difference constructed using the method of Miettinen and Nurminen. The following treatment group comparisons will be examined: each 5µg group compared to the placebo group from study V98\_06 and separately to the naïve group; the combined MF59 groups compared to the combined

placebo and naïve groups; and, the combined unadjuvanted and Alum groups compared to the combined placebo and naïve groups.

Similar analyses will be performed for the subset of subjects defined by the pre vaccination serotype-specific GBS antibody LLQ status in the V98\_06 study or V98\_06E1 study for the naïve group.

The percentages of subjects with serotype-specific concentrations above a set of pre-defined sequential serotype-specific serum antibody levels will be graphically displayed as RCDFs.

#### *Geometric Mean Concentrations*

Before any statistical analysis that assumes normally distributed observations, antibody concentrations will be  $\log_{10}$ -transformed. Individual concentrations below the limit of quantitation (LLQ) will be set to half that limit.

The logarithmically (base 10) transformed antibody concentrations will be modeled using an analysis of covariance (ANCOVA) model with a qualitative factor for vaccine group and  $\log$  (base 10) pre-vaccination concentration in study V98\_06, or V98\_06E1 for the naïve group, as a covariate. As this is a single-center study, site is not included as a covariate. Response in the V98\_06 study was different in those with a pre-vaccination concentration below the LLQ, so pre-vaccination concentration is included. The adjusted GMC and the two-sided, 95%, confidence intervals (CIs) of the GMC will be calculated based on this model. The ratio of GMCs and the corresponding two-sided, 95% CI will also be calculated based on this model. The adjusted GMC and two-sided 95% CIs will be constructed by exponentiation (base 10) of the least square means of the logarithmically transformed (base 10) antibody concentration. The model can be written as:

$$\log_{10}(y_{ik}) = \mu + \alpha_i + \beta x_{ik} + \varepsilon_{ik}$$

where  $\mu$  represents a common overall mean,  $\alpha_i$  represents the vaccine group  $i$  effect (where vaccine group is either the V98\_06 vaccine group, or naïve),  $\beta$  represents the common slope for the  $\log_{10}$  prevaccination concentration,  $x_{ik}$  for subject  $k$  in vaccine group  $i$ , and  $\varepsilon_{ik}$  represents random error for subject  $k$  in vaccine group  $i$ . A similar approach will be used in the subgroups based on pre-vaccination LLQ status.

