## 4. SELECTION OF STUDY POPULATION

### 4.1 Inclusion Criteria

In order to participate in this study, all subjects must meet ALL of the inclusion criteria described.

1. Healthy, non-pregnant subjects who have received a single 5 µg dose of GBS Trivalent Vaccine or placebo in the V98\_06 study and healthy non-pregnant female subjects aged 22-46 years inclusive on the day of informed consent who have not received any GBS vaccine in the past.
2. Individuals who have voluntarily given written informed consent after the nature of the study has been explained according to local regulatory requirements, prior to study entry.
3. Individuals in good health as determined by the outcome of medical history, physical examination and clinical judgment of the investigator.
4. Individuals who can comply with study procedures including follow-up.
5. Females of childbearing potential who are using an effective birth control method which they intend to use until the end of the study (day 181 visit) or females of non-childbearing potential.

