### **5.1.4 Randomization**

This is a single treatment open label study therefore no randomization will be carried out. The Subject ID will be the subject’s unique identification number for all CRFs and associated study documentation that will be used for duration of the study.

If for any reason, after enrolment the subject fails to undergo treatment this is an Early Termination and the reason should be recorded in source document as specified in the Source Data Agreement (SDA). The information on these Early Termination subjects should be kept distinct in the source documentation from subjects who are screen failures, as described in [section 5.1.2, Screening](#).

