### *Anti-diphtheria*

#### *Geometric Mean Concentrations*

The logarithmically (base 10) transformed antibody concentrations will be modeled using an analysis of covariance (ANCOVA) model with a qualitative factor for vaccine group and log (base 10) pre-vaccination concentration in study V98\_06, or V98\_06E1 for the naive group, as a covariate. The adjusted GMC and the two-sided, 95%, confidence intervals (CIs) of the GMC will be calculated based on this model. The ratio of GMCs and the corresponding two-sided, 95% CI will also be calculated based on this model. The adjusted GMC and two-sided 95% CIs will be constructed by exponentiation (base 10) of the least square means of the logarithmically transformed (base 10) antibody concentration. The model can be written as:

$$\log_{10}(y_{ik}) = \mu + \alpha_i + \beta x_{ik} + \varepsilon_{ik}$$

where  $\mu$  represents a common overall mean,  $\alpha_i$  represents the vaccine group  $i$  effect (where vaccine group is either the V98\_06 vaccine group, or naïve),  $\beta$  represents the common slope for the log10 prevaccination concentration,  $x_{ik}$  for subject  $k$  in vaccine group  $i$ , and  $\varepsilon_{ik}$  represents random error for subject  $k$  in vaccine group  $i$ .

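### The GMC models adjust for baseline antibody but not age, so any age effect beyond baseline antibody stays unadjusted in ratios against the non-randomised naive group

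*Combined protocol and SAP*

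**What the plan says.** Section 8.4.3.3.3 models log10 antibody concentration by ANCOVA "with a qualitative factor for vaccine group" and log10 pre-vaccination concentration as the single covariate. The group factor has a naive level: "where vaccine group is either the V98\_06 vaccine group, or naïve". The GBS and anti-diphtheria GMC models have the same form. The covariate is the V98_06 value for returning subjects and the V98_06E1 value for naive subjects.

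For GBS, the section explains the covariate choice in two respects. Response in V98_06 differed by LLQ status, "so pre-vaccination concentration is included". Site is left out with a reason: "As this is a single-center study, site is not included as a covariate". Age is not discussed. The group contrasts come from the same fit: "The ratio of GMCs and the corresponding two-sided, 95% CI will also be calculated based on this model".

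On allocation, section 5.1.4 says "therefore no randomization will be carried out". Section 1.2 acknowledges that the placebo group was randomised in V98_06 and the naive group was not, and gives the naive subjects the role of back-up controls.

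On age, section 8.4.1 provides descriptive statistics "for age, height and weight at enrolment will be calculated overall and by vaccine group". Section 4.1 admits as naive subjects "healthy non-pregnant female subjects aged 22-46 years inclusive on the day of informed consent", and the footnote to Table 3-1 ties this range to the naive group. No age range is stated for returning subjects.

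**The concern.** A GMC ratio between a returning group and the naive group is an observational comparison. The returning subjects entered a parent trial about 4 to 6 years earlier and came back; the naive subjects are recruited now. Nothing in the design aligns their ages. The 22-46 limit bounds the naive ages but does not match them to those of the returning subjects.

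Baseline antibody is the only adjustment. It covers any age effect that acts through baseline antibody, but no other. It is also measured at different points relative to this vaccination: years earlier for returning subjects, currently for naive subjects.

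What is at stake is the point estimate of a secondary ratio. With no hypothesis to test, the ratios and their intervals are the result. The naive contrasts gain weight if few placebo subjects return, which section 1.2 treats as possible. The age table in section 8.4.1 could reveal an imbalance but not show how far it moves a ratio. An adjustment chosen after seeing that table would be data-driven.

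**Working it through.** **The plan's own figure.** Table 3-1 gives five returning groups of up to 40 and 20 naive subjects: 5 × 40 + 20 = 220, which matches the stated cap. Section 8.5 gives no power, effect size or SD, so there is no sample-size calculation to reproduce.

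**Form of the bias.** In a linear model that omits age, the expected shift in the log10 GMC ratio is g × d. Here g is the age slope on log10 response given baseline antibody, and d is the mean age gap given baseline antibody. On the ratio scale the factor is 10^(g × d). Its direction depends on the signs of g and d.

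**Inputs.** The documents give neither g nor d. All values below are assumptions.

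| Slope g (log10 per year) | Gap 5 years | Gap 10 years |
|---|---|---|
| 0 | 1.00 | 1.00 |
| 0.005 | 10^0.025 = 1.06 | 10^0.05 = 1.12 |
| 0.01 | 10^0.05 = 1.12 | 10^0.10 = 1.26 |
| 0.02 | 10^0.10 = 1.26 | 10^0.20 = 1.58 |

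With no gap the factor is 1.00 whatever the slope.

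**Scale against random error.** For 40 versus 20 subjects, the 95% interval for a GMC ratio extends by a factor of 10^(1.96 × SD × √(1/40 + 1/20)) either way, and √(0.075) = 0.274. For assumed SDs of 0.5, 0.7 and 0.9 log10 the factor is 1.86, 2.38 and 3.04. The largest bias in the table, 1.58, is below the smallest of these.

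**Simulation check.** A six-group ANCOVA (5 × 40 + 20) was simulated with a true ratio of 1.00, a baseline slope of 0.5, a residual SD of 0.6 log10 and an age SD of 6 years. Naive subjects were younger by the stated gap. There were 3,000 replicates per row. The ratio is one returning group over naive.

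| g | Gap (years) | Age effect on baseline (log10 per year) | Planned model | With age | SE on log10 scale, planned → with age |
|---|---|---|---|---|---|
| 0.01 | 5 | 0 | 1.14 | 1.01 | 0.165 → 0.170 |
| 0.02 | 5 | 0 | 1.25 | 0.99 | 0.166 → 0.168 |
| 0.01 | 10 | 0 | 1.25 | 0.99 | 0.165 → 0.179 |
| 0.01 | 5 | 0.02 | 1.11 | 1.00 | 0.167 → 0.169 |
| 0 | 5 | 0.02 | 1.01 | 1.01 | 0.165 → 0.170 |
| 0.02 | 0 | 0 | 1.01 | 1.01 | 0.165 → 0.163 |

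The planned model is shifted only when both a gap and a residual age effect are present. When age acts only through baseline antibody, or when there is no gap, it is already unbiased. Adding age restores a ratio close to 1.00 at little cost in SE.

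**The case against.** A reader might infer that any age difference between naive and returning subjects carries over directly into the GMC ratios. The documents do not support that. Bias needs an age gap and also an age effect on response beyond baseline antibody, and neither is shown. That no age range is restated for returning subjects is not evidence of imbalance, because their ages were set by a parent protocol that is not among these documents.

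A reader might also point to chance. For 40 versus 20 subjects, random sampling alone gives a 95% range of ±1.96 × √(1/40 + 1/20) = ±0.54 SD in mean age. The effect of such chance imbalance is part of the residual error that the model's interval already reflects. It is not evidence of confounding.

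Nor are these the study's main contrasts. The primary immunogenicity endpoint is the day 61 percentages reaching the antibody levels. GMCs are secondary, all analyses are descriptive and there is no success criterion. The GMC text does not list which ratios will be formed. Section 1.2 discloses that the naive group lacks the placebo group's randomised origin and calls the study exploratory.

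Finally, age is not the only candidate. Section 5.1.2 collects receipt of diphtheria-containing vaccine, which is an obvious covariate for the anti-diphtheria model. An age term would not make the naive contrasts randomised, and it leaves the primary percentage comparisons unadjusted.

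All of this stands, and it limits the point to a modest one. It does not remove the gap: the naive ratios have no age adjustment, age is available, and its omission is not explained.

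**Conclusion.** The point holds as a minor improvement. Both GMC models leave unadjusted any age difference between naive and returning subjects that affects response beyond baseline antibody. The bias may be nil. Under the assumed non-zero slopes and gaps it is a factor of about 1.06 to 1.58, within random error but able to move a point estimate without being visible in the ratio or its interval.

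Only contrasts that use the naive group are affected by this mechanism. Contrasts with V98_06 placebo start from randomised groups and are less exposed, although selective return could still unbalance them. No formal conclusion changes, because none is planned. Confidence that a material bias exists is low; that the models contain no age term is plain from the text.

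**What to change.** In section 8.4.3.3.3, pre-specify a sensitivity ANCOVA that adds age at enrolment as a continuous covariate to the GBS and the anti-diphtheria GMC models. Report the GMC ratios against the naive group with and without it, beside the age summary from section 8.4.1. The planned models can remain the main analysis.

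The cost is one variable already collected and one residual degree of freedom: at full enrolment 220 − 6 − 1 = 213 becomes 212, and fewer in the per-protocol set. In the simulated cases with an age gap, the SE rose from about 0.165 to 0.17-0.18 log10. No extra data or visits are needed.
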